We will begin Specific Aim #3 after a 3-month lead in phase, during which we ensure that all performance targets from Specific Aim #2 are being reliably measured. This aim will include administration of a series of patient, caregiver, and provider surveys as well as analysis of the quality benchmarks mentioned above. Specifically, we propose to perform a prospective, matched cohort comparative effectiveness study of eligible patients receiving care within the multidisciplinary environment versus matched controls concurrently receiving usual, serial care in the same healthcare system.

Eligibility criteria:

Multidisciplinary cases will have an untreated but biopsy-confirmed lung cancer diagnosed, preferably within 8 weeks of screening for study eligibility. Therefore, patients will still need either a staging evaluation or selection of first line therapy, the types of decision-making most often required in lung cancer care.

Controls will be selected from the pool of patients receiving usual ('serial') care within the same institution. Two serial care controls will be matched to each multidisciplinary care case. To be eligible for inclusion, a serial care patient must have an untreated biopsy-confirmed lung cancer, diagnosed preferably within an 8 week window surrounding the diagnosis of the case to whom he/she will be matched (4 weeks prior through 4 weeks after the case's diagnosis), and will be matched hierarchically based on several matching criteria: clinical stage, performance status, insurance status, race, and age range.

All multidisciplinary clinic patients will be screened for eligibility before their initial clinic visit. If a patient is determined to be eligible to participate in Specific Aim #3, they will be approached for consent to the study by the clinical research professionals during their initial visit.

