Potential serial care patients will be pre-screened for matching eligibility by the above criteria before a multidisciplinary patient has consented to participate in the study. However, potential serial care patients will not be approached for consent until after a matching multidisciplinary patient has consented to participate in this study. Each week, a list of potential matching serial care patients will be provided to the thoracic oncology research group by Baptist Health Information Management (HIM). Patients are included on this list based on an algorithm of specific ICD-9 diagnosis and CPT procedure codes that are potential identifiers of lung cancer patients who fit the matching criteria of this specific aim. Multidisciplinary clinic staff will pre-screen from the list provided by HIM on a regular basis to identify potential serial care matches. Once a multidisciplinary patient has consented to the study, these potential serial care matches will be prioritized by closest adherence to the matching criteria of the corresponding multidisciplinary patient. This list of potential serial care matches will be supplemented by lists of new lung cancer patients provided by the treating groups (medical oncology,

radiation oncology, surgery) within the Baptist healthcare system. Any potentially eligible serial care patient will then be communicated to the clinical research professionals. The clinical research professionals will then work through the list to find and consent up to two serial care patients, along with their caregivers, to the prospective comparative study.

For clinical provider feedback, we will survey clinical providers referring patients into the multidisciplinary thoracic oncology clinic and providers actively participating in the multidisciplinary thoracic oncology clinic.

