Models for categorical outcomes: Assuming Y_i represents whether the patient receives stage-appropriate care (yes/no), and G_i represents whether patient is in multidisciplinary program or matched control, and X_i represents other confounders except matching variables. The conditional fixed effect model can be expressed as $\text{Log}(p(Y_i=1)/p(Y_i=0)) = \beta * G_i + \gamma X_i$. Note that intercept and matching variables are not estimated. The exponent of β is the odds ratio of receiving stage-appropriate care between multidisciplinary v. control. For other categorical outcomes, models and interpretations are similar.

Models for timeliness of care: The timeliness of care is measured in days: for example, days from the first diagnostic imaging test (earliest date of chest X-ray or CT scan) to receiving the actual treatment (surgery, chemotherapy, radiation, or hospice care); days from the first diagnostic imaging test to multidisciplinary clinic visit, and days from multidisciplinary clinic visit to treatment commencement. These variables are inherently right skewed and can be fit with Gamma distribution. In the fixed effects generalized linear model, $\text{Log}(\text{days}_i) = \beta * G_i + \gamma X_i$, the shape and scale parameters of the gamma distribution will be empirically determined based on all observations in each group. The exponent of β is the geometric mean difference of days (similar to median difference) between multidisciplinary program and controls.

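### Cases and serial controls must be untreated on different, partly undefined dates, and the timeliness model makes no allowance for this, so the comparison is biased in a direction the documents do not settle

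*Protocol*

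**What the plan says.** **Cases** (Protocol, Eligibility criteria). "Multidisciplinary cases will have an untreated but biopsy-confirmed lung cancer diagnosed, preferably within 8 weeks of screening for study eligibility". Once found eligible, "they will be approached for consent to the study by the clinical research professionals during their initial visit".

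**Controls** (same section). To be eligible, "a serial care patient must have an untreated biopsy-confirmed lung cancer", with diagnosis preferably in the window "4 weeks prior through 4 weeks after the case's diagnosis". The order of events is: "Each week, a list of potential matching serial care patients will be provided"; "Potential serial care patients will be pre-screened for matching eligibility by the above criteria before a multidisciplinary patient has consented"; and "potential serial care patients will not be approached for consent until after a matching multidisciplinary patient has consented to participate in this study". Staff then rank the candidates, and the research professionals work through the list.

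**Date of the check.** No sentence says when a control must be untreated, whether status is rechecked at approach, or what happens to a pre-screened patient who starts treatment in the meantime.

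**Analysis.** Timeliness is listed under Main outcomes to be measured. Models for timeliness of care fits a gamma generalized linear model with log link. Its first example of an outcome is "days from the first diagnostic imaging test (earliest date of chest X-ray or CT scan" and so on, up to actual treatment. No delayed entry or landmark is described. The Benchmarks/Endpoints list uses a different clock, which starts at enrollment.

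**SAP** (Statistical Methods (Supplemental)). Individual matching is replaced by frequency matching. The text does not mention consent order or the date for judging treatment status.

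**The concern.** A patient who must be untreated on some day after diagnosis is in the data only because treatment had not started by that day. Counting time from imaging or diagnosis as if everyone had been observed from then inflates the apparent wait, and a later check inflates it more. If both arms were checked at the same point on their own clocks, the inflation would largely cancel. Here they are not. A case is checked around the clinic visit. A control is checked either at pre-screening or after another patient's consent plus a recruitment lag. The arms can therefore differ in observed days to treatment when true waits are identical. Matching on stage, performance status, insurance, race and age does not touch this, because none of these is the entry date.

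At stake is the imaging- or diagnosis-origin comparison of timeliness, one of the study's main outcomes.

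**Working it through.** The plan states no waiting-time distribution and no approach lag, so there is no figure of its own to reproduce. All inputs below are assumptions except the ±4-week window, the 8-week limit and the weekly list.

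**1. Effect of one check date.** For gamma time T with shape 2 and mean 60 days (scale 30), and x = c/30:

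E[T | T > c] = 60 × (1 + x + x²/2) / (1 + x)

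- c = 14: 60 × 1.5756/1.4667 = 64.45 days
- c = 21: 60 × 1.9450/1.7000 = 68.65 days
- c = 28: 60 × 2.3689/1.9333 = 73.52 days
- c = 42: 60 × 3.3800/2.4000 = 84.50 days

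If cases were checked on day 14 and every control 7 to 28 days later, controls would look 68.65/64.45 − 1 = 6.5% to 84.50/64.45 − 1 = 31.1% slower. That presumes controls are always checked later, which the plan does not say.

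**2. The plan's entry rules, with no true difference.** Simulation, in days from diagnosis:

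- T: the same gamma in both arms, shape 2 or 3, mean 45 or 60
- case visit W: uniform from day 3 to day 28 or 56; a case is kept if T > W
- control diagnosis minus case diagnosis, D: uniform on −28 to +28
- lag L from case consent to control approach: 0, 0-14 or 7-28 days
- control kept if T > max(W − D + L, 0) when checked at approach, or if T exceeds a 0-7 day list delay when checked only at pre-screening

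Control mean relative to case mean, over the four shape and mean combinations:

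| Control check | Case visits | L (days) | Controls look |
|---|---|---|---|
| Approach | within 8 weeks | 0 | 1.5-6% faster |
| Approach | within 8 weeks | 0-14 | 0.6% faster to 2.3% slower |
| Approach | within 4 weeks | 0 | 0.7-2.3% slower |
| Approach | within 4 weeks | 0-14 | about 6% slower |
| Approach | within 4 or 8 weeks | 7-28 | 8-16% slower |
| Pre-screen only | within 4 or 8 weeks | n/a | 4-22% faster |

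I reran this grid and it agreed to within about half a percentage point. For the two middle combinations (shape 2 with mean 60, shape 3 with mean 45) the range is about 4% faster to 14% slower at approach, and 7-18% faster at pre-screening.

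**3. A second distribution.** Lognormal times, true median 6 weeks, log-SD 0.6, with the lag added for every control. Median weeks to treatment for lags of none, 0-2 and 1-4 weeks:

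- Visits within 4 weeks: cases 6.4; controls 6.7, 7.1, 7.9
- Visits within 8 weeks: cases 7.5; controls 7.2, 7.6, 8.5
- Pre-screen only: controls 6.0 against cases 6.4 and 7.5

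The sign pattern is the same. The largest gap is 7.90/6.36 = 1.24 on the median, so 14% is not a ceiling.

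**4. Does delayed entry repair it?** Shape 2, mean 60, visits on days 3-28, status checked at approach; the true median is 50 days. Unadjusted medians are 55.5 for cases and 57.6, 60.8 and 66.6 for controls at the three lags. The delayed-entry Kaplan-Meier median returned to 50 days in both arms.

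**5. Clock.** The simulation starts at diagnosis. If the imaging-to-diagnosis interval is alike in both arms and independent of the later wait, starting at first imaging keeps the gap in days but shrinks the percentages.

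**The case against.** **The drop-out of controls is inferred.** Pre-screening uses the same criteria and precedes case consent, so status may be settled then and never revisited. This stands. It does not remove the problem, because that reading leaves cases filtered at the visit and controls almost unfiltered, and the bias runs the other way.

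**Cases pass a filter too, and controls may be diagnosed up to four weeks after the case.** Both stand. Only the difference between arms counts, and with late case visits and no lag it reverses.

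**A reader might infer that fast-treated serial patients are lost and the design therefore favours multidisciplinary care, by 31-35% at worst.** The documents do not support that. The 31% comes from fixing cases at day 14 and always adding time for controls (step 1). The 35% comes from filtering controls alone after 28 days, which is not a between-arm comparison.

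**The enrollment clock in Benchmarks/Endpoints behaves differently.** This stands. Under the step 1 gamma, the mean remaining wait is 64.45 − 14 = 50.5 days after entry on day 14, and 73.52 − 28 = 45.5 after day 28. Later entry shortens it, so the point is confined to the imaging or diagnosis origin.

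**Timeliness is neither the primary endpoint nor one of the six numbered endpoints.** True, but it is a listed main outcome with its own model.

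**Conclusion.** The concern holds as a defect of undetermined sign. Both arms must be untreated at entry, the entry dates are set differently and partly left open, and the imaging-origin model ignores the resulting left truncation. With no true difference, controls look about 4% faster to 14% slower if checked at approach (6% faster to 16% slower over all four gamma combinations), and about 7-18% faster (4-22%) if checked only at pre-screening. These figures depend on assumed waiting times, visit dates and lags, and are illustrations rather than bounds. A bias reliably in favour of multidisciplinary care is not established. Nothing is claimed here about the size of any effect on survival, the primary endpoint.

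**What to change.** 1. **Analysis.** Treat imaging- or diagnosis-origin timeliness as time to event. Keep the origin as the time scale and enter each patient, in both arms, into the risk set on the date untreated status was verified. A common landmark, with the comparison confined to patients untreated at it, is the alternative.
2. **Definition.** State one index-date rule for untreated status and apply it to both arms. Do not move only the controls' check to pre-screening; that produces the 7-18% tilt in the other direction.
3. **Reporting.** Give the number of pre-screened controls lost because treatment began before approach.

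The SAP describes conduct in the past tense. Items 1 and 3 remain possible after enrollment if the dates were kept.

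**Cost.** A time-to-event model replaces or supplements the gamma model. Intervals widen somewhat. Early risk sets may be small, and where nobody in an arm enters before a given day the curve is conditional on being untreated on that day. The verification date must be recorded or recovered for each patient; pre-screening, clinic-visit and consent dates arise in the course of the study and should supply most of it.

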REACH – To evaluate the reach of the multidisciplinary clinic, we will collect extensive data on all patients participating in Specific Aim #3. These data will cover the full timeline of a patient’s care for lung cancer, including details of their history of lung-cancer-related care prompting their entry into the healthcare system, of their experience within the system, of their expected treatment and their actual received treatment, and finally the outcome of their treatment. These data will be analyzed to define the characteristics of multidisciplinary patients versus serial care patients, which will in turn address questions about the reach of the multidisciplinary clinic (i.e., what kinds of patients are likely to come into contact with multidisciplinary care and what kinds of patients do not?).

EFFECTIVENESS – In order to evaluate the effectiveness of the two models of care, we will analyze the data referenced in the Reach component. We will also administer surveys to all participating patients, their caregivers and their clinical providers. We will test our ability to obtain patient, caregiver, and clinical provider feedback using several instruments (specific questions will be drawn from the attached self-report patient, caregiver, and clinical provider measures and tailored to each stakeholder group as appropriate).

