- consensus management recommendations

Multidisciplinary clinic experience

- date of clinic visit
- details of patient experience in clinic
- treatment decisions made

Tumor characteristics (pre and post-op)

- details of T-category
 - 1) tumor size
 - 2) tumor laterality
 - 3) site of tumor invasion (if any)
- details of N-category
 - 1) number and details of suspected lymph nodes
 - 2) number and details of pathologically examined lymph nodes
- details of M-category: location and details of metastatic disease (if any)
- histology
- grade
- cumulative AJCC staging (clinical and pathologic)

Details of treatment

- surgery
- chemotherapy
- radiation therapy
- palliative/hospice care only
- timeline and outcomes of therapy

Benchmarks/Endpoints

- Patient survival** – as measured from the time from cancer diagnosis to death or data censor.
- Timeliness of care** – aggregate time from enrollment to specific care delivery endpoint; compared to British Thoracic Society recommendations.
- Thoroughness of staging** – proportion of patients with histologically confirmed (i.e., biopsied) stage-defining lesion

Appropriateness of treatment selection – Stage I or II: surgery (or radiation therapy with documented contraindication to surgery or patient refusal) Stage III: chemotherapy and radiation therapy with or without surgery Stage IV: systemic therapy (or palliative care with documented patient refusal or contraindication to systemic therapy)

Timeliness of communication – official, verifiable communication of management decisions with providers inside and outside the multidisciplinary program and official, verifiable communication of management plans with patients and their care-givers.

Survey response rate – for patients, for caregivers, for clinical providers; number of responses versus number administered

Survey responses –measured by qualitative analysis of completed surveys

Inclusion criteria

All patients who undergo care for lung cancer or an undiagnosed lung mass within the Baptist Memorial Health Care Corporation's hospitals from January 1, 2009 until the end of the defined study period will be eligible for inclusion in the data collection for this study. In addition, caregivers of patients within the same institution and within the study window, clinical care providers (doctors and nurses) who have taken care of patients within the eligible institutions during the study window.

Exclusion criteria

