Patients who do not have a biopsy-confirmed lung cancer are excluded from this study.

Vulnerable populations

No vulnerable populations will be included in this study.

Length of study

Generally, this project is funded by a 3-year grant, which starts on February 3, 2014 and ends on February 2, 2017, with the possibility of extension by up to 1 year (February 2, 2018). However, because of the need to demonstrate program sustainability, we will continue to measure the quality benchmarks that constitute specific aim 2, as a key ongoing quality improvement exercise for the clinical multidisciplinary program. In addition, because of the primary endpoint, overall survival, it may be necessary to continue long-term follow up of patients for up to 5 years after enrollment of the final patient in specific aim 3, the comparative effectiveness study.

Number of study sites

Specific Aim #3 involves the Baptist Memorial Health Care Corporation system.

Number of subjects

Specific Aim #3 will match 150 patients undergoing care in the multidisciplinary clinic with up to 300 similar patients concurrently undergoing serial care for a total of 450 patients.

However, for the process engineering sub-aim, and to examine the domains of Reach and Adoption, all patients who receive lung cancer care from January 1, 2009, onward, and the clinical providers of lung cancer care, will need to be accessible for limited data abstraction.

Sample size calculation

150 multidisciplinary clinic patients matched 1:2 with 300 serial care patients = 450 patients for Specific Aim #3. The 150 multidisciplinary clinic patients will all be selected from the estimated 960 patients examined in Specific Aim #2. We powered the prospective comparative cohort study in Specific Aim #3 based on the survival analysis. Assuming power = 80%, alpha= 0.05, two sided test, mortality rate 40%, and hazard ratio 1.25, we estimate the total sample size 427 using Cox regression procedure in PASS 11. Since Baptist Health Care System manages >800 new cases each year, 300 of which are expected to be seen in multidisciplinary clinic, in practice, we conservatively expect to be able to recruit 150 cases from multidisciplinary clinic and 300 matched serial care controls (1:2 match) in 18 months.

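### Reach is given two populations, and the only comparison stated for it uses the matched Aim 3 sample, which cannot show who reaches the clinic on the matched factors

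*Protocol*

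**What the plan says.** Two parts of the Protocol assign a population to Reach.

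- **Methods or procedures, REACH.** The source is Aim 3: "To evaluate the reach of the multidisciplinary clinic, we will collect extensive data on all patients participating in Specific Aim #3". The comparison follows: "These data will be analyzed to define the characteristics of multidisciplinary patients versus serial care patients". Its purpose is to learn "what kinds of patients are likely to come into contact with multidisciplinary care and what kinds of patients do not". The EFFECTIVENESS paragraph then reuses the same data, which confirms that the Aim 3 dataset is meant.
- **Number of subjects.** After giving the matched sample of 150 and up to 300, the section turns to a wider group: "to examine the domains of Reach and Adoption, all patients who receive lung cancer care from January 1, 2009, onward". These patients "will need to be accessible for limited data abstraction". No comparison, variable list or method is attached. The Inclusion criteria agree on scope: patients treated in the system's hospitals since 2009 "will be eligible for inclusion in the data collection for this study".

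Under Eligibility criteria, a serial patient "will be matched hierarchically based on several matching criteria: clinical stage, performance status, insurance status, race, and age range". Candidates are ranked by how closely they fit a consented case, and are approached only after that case has consented. The SAP (Statistical Methods, Supplemental) reports that individual 1:2 matching did not deliver good matches in time. It replaces it with frequency matching and handles age, together with sex and histology, as a model covariate. Neither the Protocol's Statistical analysis section nor the SAP specifies a Reach analysis.

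**The concern.** Reach asks how clinic patients differ from those who never get there. A control group recruited because it resembles the clinic patients on a factor cannot answer that for the factor concerned: the controls' distribution reflects the recruitment rule, not the referral pattern. The affected factors include race and insurance, where unequal access would matter most, and the Study design section lists equity among the quality dimensions to be covered. A table showing similar race and insurance profiles in the two arms could be taken as evidence of even access when it shows only that the matching worked.

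Consent adds a second filter. Both arms contain only people who were approached and agreed, and serial patients enter only if a similar case enrolled first.

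**Working it through.** There is no Reach figure in the documents to reproduce. The check has two parts.

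**1. The two populations side by side**

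| | REACH paragraph | Number of subjects |
|---|---|---|
| Who | Aim 3 participants | All lung cancer patients from 2009 |
| Selection | Consented; controls matched to cases | None stated |
| Depth of data | Extensive | Limited; variables not listed |
| Comparison stated | Multidisciplinary versus serial | None |

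The Adoption domain is a useful contrast. There the Protocol compares the program's referral records with the list of relevant credentialed specialists, so the denominator is unmatched. Reach has no equivalent sentence.

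**2. How far matching shrinks a difference (illustration)**

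Inputs from the Protocol (Sample size calculation): more than 800 new cases a year, 300 of them expected in the clinic; 18 months of recruitment; 150 cases and 300 controls. Over 18 months this gives 300 × 1.5 = 450 clinic patients and at least (800 − 300) × 1.5 = 750 others. Aim 3 would hold 150/450 = 33% of the first group and 300/750 = 40% of the second.

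Assumed, because the documents give no shares: a factor is held by a share p_c of clinic patients and p_s of all serial patients. A share m of controls is matched exactly on it, and the rest are a random draw from the serial pool.

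- Expected control share: p_ctrl = m·p_c + (1 − m)·p_s
- Expected difference: p_c − p_ctrl = (1 − m)(p_c − p_s)
- Odds ratio: [p_c/(1 − p_c)] / [p_ctrl/(1 − p_ctrl)]

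Example with p_c = 0.30, p_s = 0.40, m = 0.8: p_ctrl = 0.8 × 0.30 + 0.2 × 0.40 = 0.32, and the odds ratio is (0.30/0.70)/(0.32/0.68) = 0.91. The true value is (0.30/0.70)/(0.40/0.60) = 0.64.

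| p_c, p_s | True odds ratio | m | p_ctrl | Odds ratio seen | Power, 150 vs 300 |
|---|---|---|---|---|---|
| 30%, 40% | 0.64 | 100% | 30% | 1.00 | no difference left |
| | | 80% | 32% | 0.91 | about 6% |
| | | 50% | 35% | 0.80 | about 18% |
| 20%, 40% | 0.375 | 100% | 20% | 1.00 | no difference left |
| | | 80% | 24% | 0.79 | about 15% |
| | | 50% | 30% | 0.58 | about 62% |

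Power is for a two-sided comparison of two independent proportions at 0.05. With about 450 clinic patients against 750 others, the unmatched comparison keeps the full difference and has about 94% power for 30% versus 40%, and close to 100% for 20% versus 40%.

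The quantity that decides the bias is m. The documents do not give it, and it may differ between factors because the matching is hierarchical.

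**The case against.** The strongest reply is that the plan already provides the right cohort. The Number of subjects section sets Reach apart from the matched sample, and the REACH paragraph never says that only Aim 3 data will be used. The two can be read together as rich data on participants plus basic data on everyone, in which case the defect is a missing cross-reference. This stands in part: it defeats any claim that the plan is bound to the matched analysis. It does not remove the problem, because making records accessible is not an analysis, and the one comparison that is written down draws on Aim 3 participants.

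A reader might also infer that controls are made equal to cases, so that Reach disparities are sure to be hidden. The documents do not support that. Matching is hierarchical and by best available fit, the SAP says good individual matches were not attained, and age became a covariate. Stratifying an analysis also does not by itself equalise the arms' overall distributions. The consequence is attenuation of unknown size rather than certain erasure, and that still leaves the arm difference uninterpretable as Reach.

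Unmatched characteristics in the Protocol's data list, such as sex, zip code, comorbidities, smoking history and method of detection, can still be compared in Aim 3. Consent selection remains, and matching may weaken those correlated with the matched factors.

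**Conclusion.** The point holds as an inconsistency to be reconciled. Two sections name different populations for Reach, and the only stated comparison uses a sample that cannot show access differences by clinical stage, performance status, insurance or race. Under the Protocol's matching the same applies to age range; under the SAP age is less affected.

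The size cannot be derived from the documents. The odds ratios above rest on assumed shares and assumed matching rates. An extreme example, with 25% of clinic and 40% of serial patients, takes a true odds ratio of (0.25/0.75)/(0.40/0.60) = 0.50 to 1.0, but only if matching is perfect, which the SAP indicates it was not. A reader might infer that a false finding of equitable access is built in; that would require the sponsor to ignore the all-patient cohort the plan itself provides.

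The stakes are modest. Reach is not among the six endpoints in the Study design section, and overall survival is primary. The survival comparison is unaffected.

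**What to change.** - In the REACH paragraph, state that Reach compares all clinic attenders with all non-attenders in the unmatched cohort described under Number of subjects, restricted to the period when the clinic was open. The documents give no opening date, so it should be stated.
- List clinical stage, performance status, insurance, race and age among the variables abstracted for that cohort.
- Name the analysis, for example shares by group with confidence intervals and a logistic model for clinic attendance.
- Present the Aim 3 comparison of matched factors as a balance table and say that it is not Reach evidence. Unmatched factors may be described there with a note on consent selection.

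The cost is mainly wording, since abstraction on all patients is already foreseen. The downside is that abstracted records are less rich than data from consented patients, and performance status may be incomplete, so its missingness should be reported by group.
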